### **2.3.4. Potential Benefits**

Study participants may benefit by learning about RSV vaccination, eligibility, and navigation to vaccination. The benefits for the community may include adapted strategies to increase vaccine uptake in a community disproportionately impacted by respiratory viruses and with historically lower rates of vaccine uptake compared to non-Latino White populations.

The minimal risks to subjects are reasonable in comparison to the potential benefits to themselves and their community by improving RSV vaccine uptake. The RSV vaccine is FDA-approved and we will only enroll participants who are eligible for RSV vaccination per the CDC and ACIP.

### 2.3.5. Importance of the Knowledge to be Gained

The minimal risk in this study is far outweighed by the importance of the knowledge to be gained. The overall objective of the study is to inform effective, actionable, and customizable community-based strategies to increase RSV vaccine uptake among Latino older adults, with generalizability to other vaccines and settings. Findings from this study will fill key knowledge gaps about vaccine promotion in communities that experience health disparities: (1) effectiveness of high vs. low-intensity CHW counseling interventions, (2) implementation and impact of text-message from trusted community-based organizations, as opposed to health systems, (3) effectiveness of cross-generational social network strategies, ie. empowering grandchildren to discuss vaccines with grandparents, (5) facilitators and barriers to adapting interventions that were effective in a pandemic to the non-pandemic setting, where urgency and resources are lower.

## 3. Study Objectives and Endpoints

### 3.1. Primary Objectives

Our overall study objective is to assess the effectiveness and implementation of the Unidos en Salud (UES) 'Motivate, Vaccinate, Activate' strategy, which includes CHW counseling and text-messaging on increasing RSV vaccine uptake among older Latino adults. Our primary hypothesis is that language- and culturally-concordant CHW motivation and activation counseling sessions, coupled with text message nudges, will increase RSV vaccine confidence by addressing trust, knowledge, and access-related barriers. To achieve this objective, we will first adapt the key intervention components in Aim 1, then will determine the effectiveness of a multicomponent intervention (CHW counseling and text-message nudges) on increasing vaccine uptake in Latino older adults (Aim 2) and encouraging Latino adults (18-49 years) to discuss RSV vaccination among older adults in their family and social networks (Aim 3). The primary outcomes are summarized in Table 1.

The Study Aims are:

**Aim 1: Adapt a CHW counseling and text-message intervention to increase RSV vaccine uptake and activate younger adults to discuss RSV vaccination with older adults in their social networks.** In this developmental aim, we will use the ADAPT-ITT framework to adapt two intervention components CHW counseling and text-messages nudges, to increase RSV vaccine uptake in Latino older adults ( $\geq 50$  years)

**Aim 2: Determine the effectiveness of CHW counseling and text-message nudges from a CBO on RSV vaccine uptake among Latino older adults.** In a randomized two-arm trial, will compare CHW counseling and text message nudges vs. CHW delivered RSV vaccine flyer + text-message nudges in 400 Latino adults  $\geq 50$  years. Study interventions are adapted in Aim 1a. Our hypothesis is text messages coupled with a community health worker counseling session will increase RSV vaccine uptake compared to texts alone. Primary Outcome: RSV vaccine uptake at 60 days. Secondary outcomes include change in motivation to get and confidence in the RSV vaccine, implementation per the RE-AIM framework, with a focus on implementation, adoption and maintenance assessed via mixed methods.

**Aim 3: Determine the effectiveness of CHW 'activation' counseling and text-message nudges from a CBO on activating adults to discuss RSV vaccination with older adults in their social network.** In a parallel design to Aim 2, we will compare: CHW 'activation' counseling and text message nudges vs. RSV vaccine flyer at enrollment + text-message nudges in 350 Latino adults (18-49 years). Study interventions will be adapted in Aim 1b. Our

hypothesis is text messages coupled with CHW counseling will activate participants to discuss RSV vaccination with older adults in their network, compared to text-message alone. Our primary outcome is average proportion of older adult ( $\geq 50$  years old) network contacts with whom RSV vaccination was discussed. Secondary outcomes include change in knowledge about the RSV virus and the vaccine, change in motivation to discuss the RSV vaccine with eligible family members or friends, implementation per the RE-AIM framework, with a focus on *implementation, adoption, and maintenance components* assessed via mixed methods

**Table 1: Primary Objectives**

Primary Objective	Endpoint(s)	Time Frame
1. Aim 1 (Developmental Aim) -Community-based survey on RSV vaccine hesitancy -Community advisory group adapts intervention components. -In depth interviews	N/A	1 year
2. Aim 2 (Motivate Trial): Determine the effectiveness of CHW counseling and text-message nudges from a CBO on RSV vaccine uptake among Latino older adults.	RSV Vaccine uptake at 60 days per California Immunization Registry (CAIR) or per medical record	60 days from time of intervention
3. Aim 3 (Activate Trial): Determine the effectiveness of CHW 'activation' counseling and text-message nudges from a CBO on activating adults to discuss RSV vaccination with older adults in their social network .	Self-reported average proportion of social network contacts $\geq 50$ years with whom participant discussed RSV vaccination at 60 days.	60 days from time of intervention

### 3.2. Secondary Objective(s)

#### Aim 1 (Development aim).

- **Secondary:** Predictors of RSV Vaccine hesitancy, Adaptation of text-message and CHW counseling intervention with Community Advisory Board.

#### Aim 2:

##### **Secondary:**

- RSV Vaccine uptake at 60 days (self-report)
- RSV Vaccine uptake at 90 days per CAIR or per medical record
- RSV Vaccine uptake at 6 months per CAIR or per medical record
- Median time to vaccination (days)
- Appointment made at 60 days in clinic or a pharmacy with intent to get RSV Vaccine per self-report
- Increase in RSV Vaccine confidence (BeSD indicator) by 1 point

- Increase in motivation to get RSV Vaccine (BeSD indicator) by 1 point
- Increase in RSV vaccine knowledge by 1 point (Likert scale): Before today how much did you know about the RSV vaccine (1 = nothing, 2= a little, 3= some, 4= a lot)
- Average proportion of social network contacts  $\geq 50$  years with whom participant discussed RSV vaccination at 60 days.
- Implementation outcomes per Reach Effectiveness Adoption Implementation Maintenance (RE-AIM) framework (Table 2)

Aim 3:

Secondary:

- Discussed RSV vaccination with  $\geq 1$  eligible family member or friend within 60 days of enrollment
- Implementation outcomes per Reach Effectiveness Adoption Implementation Maintenance (RE-AIM) framework (Table 2)
- Increase in RSV Vaccine confidence (BeSD indicator) by 1 point
- Increase in motivation to discuss the RSV Vaccine with eligible family members or friends(BeSD indicator) by 1 point
- Increase in confidence in the RSV Vaccine (BeSD indicator) by 1 point
- Increase in RSV vaccine knowledge by 1 point (Likert scale): Before today how much did you know about the RSV vaccine (1 = nothing, 2= a little, 3= some, 4= a lot)

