#### 4.3.5. Duration of study procedures

The duration of study procedures is 90 days, but participants can be in the study up to 24 months from enrollment if they are selected for in-depth interviews.

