**Ascertainment of vaccination status:** Vaccine status will be ascertained prior to text nudge and at 60 and 90 days through the medical record or California Immunization Registry (CAIR), the medical record, or proof of vaccination from a pharmacy.

**Semi-structured IDI with participants:** In accordance with principles of Grounded Theory, we will iteratively collect and rapidly analyze interview transcript data, continuing to select

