## 9.2. Aim 2 (Motivate Trial) Statistical Considerations

**Study Design:** Two-arm randomized type-1 effectiveness-implementation individually randomized trial.

**Analysis Plan.** We will compare the primary outcome of RSV vaccine uptake within 60 days between the two study arms using two broad statistical approaches: unadjusted analyses to explore average treatment effects and model adjusted estimates to reduce variance and examine effects for subpopulations. First, we will examine the intention-to-treat (ITT) effect, over all participants, for the primary outcome of vaccine uptake using the Fisher exact test. To account for participants which the CHW may not be able to reach, we will examine the average treatment effect on the treated (ATT). Second, we will use targeted maximum likelihood estimation (TMLE), a pre-specified approach to data-adaptively adjust for stratified randomization factors and additional baseline predictors of the outcome in order to improve precision. RSV vaccine uptake will be ascertained through the California Immunization Registry, the medical record, or proof of vaccination from a pharmacy. Using an analogous approach, we will also compare intervention effectiveness on pre-specified secondary outcomes and within pre-specified subgroups: baseline high vaccine hesitancy, low trust of healthcare system, low acculturation (score<3.0), sex. These will be augmented by predictor analyses to elucidate risk factors for poor vaccine uptake, overall and by arm and exploratory machine learning analysis for treatment effect heterogeneity. Additionally, we will examine pathways of intervention action (i.e. direct and indirect effects) using formal mediation analyses, considering mediation by post-baseline trust and perceived benefits in the vaccine. Both predictor and mediation analyses will use TMLE.

**Implementation Outcomes:** We will calculate implementation outcomes using the RE-AIM framework for each, through quantitative and qualitative analyses.

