### 9.2.1. Aim 2 Sample Size Considerations

Based on our preliminary data and a national survey, we anticipate 28% RSV vaccine uptake in our text-only arm (20% with no intervention and 8% increase with text). Assuming complete data for the primary outcome of vaccine uptake reported by CAIR, the medical record, or proof of vaccination from a pharmacy and  $\alpha=0.05$ , our sample size of N=200 per arm will conservatively

provide a minimum detectable ITT effect size of 10%. Assuming CHWs will be able to reach 90% of participants assigned to the counseling arm, our sample will be able to provide a minimum detectable ATT of 10.9%; if participants assigned to counseling are particularly hard to reach and only 80% take part in CHW counseling, we will be able to provide a minimum detectable ATT effect 12.3%.

Statistical power for secondary outcomes will depend on participation in the 60-day follow-up survey. If 10% of participants are lost to follow-up, the minimum detectable effects increase to 10.6% for ITT, 11.5% for ATT if 90% of intervention arm participants receive counseling and 12.9% for ATT if 80% of intervention arm participants receive counseling. Under a setting of high loss to follow-up, where 20% of participants in both arms are not reached for a follow-up survey, the minimum detectable effects increase to 11% for ITT, 12.2% for ATT if 90% of intervention arm participants receive counseling and 13.7% for ATT if 80% of intervention arm participants receive counseling.

Estimated treatment effects for all outcomes will be improved with statistical modeling with TMLE.

In a nested secondary pre-post analysis we will compare the proportion of people who received the RSV vaccine prior to the text-message to 30 days after the text.

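### At the anticipated 28% text-arm uptake by day 60, an all-randomized median time to vaccination is not expected within the 90-day procedures, and the 6-month look-up that might reach it is listed only in Section 3.2

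*Protocol*

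**What the plan says.** - Section 3.2, Aim 2, lists "Median time to vaccination (days)" among the secondary endpoints. It names no horizon and does not say whether the median is over all randomized or only the vaccinated.
- Section 9.2.1 states "we anticipate 28% RSV vaccine uptake in our text-only arm (20% with no intervention and 8% increase with text)." Section 9.2 ties that rate to a time point: "We will compare the primary outcome of RSV vaccine uptake within 60 days between the two study arms."
- Section 4.3.5 says "The duration of study procedures is 90 days"; longer participation is foreseen only for people selected for in-depth interviews. Section 7.2.1.1 says "Vaccine status will be ascertained prior to text nudge and at 60 and 90 days."
- Section 3.2 also lists uptake at 6 months from the registry or medical record. Table 3 repeats the median and the 90-day uptake but not the 6-month uptake, and Section 7.2.1.1 schedules no 6-month look-up.
- For the counseling arm, Section 9.2.1 gives no anticipated rate. It says only that the sample will "provide a minimum detectable ITT effect size of 10" percent.

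**The concern.** The protocol fixes the summary measure as a median, while its own planning rate puts the text arm well short of half vaccinated at the time of the primary outcome. If follow-up for this endpoint ends with the 90-day procedures, the likely result in that arm is that the median was not reached, and the endpoint then yields no numerical contrast between arms.

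The obvious fallback is worse. A median among vaccinated participants can always be computed, but being vaccinated is the outcome that the intervention is meant to change. The two groups compared would no longer be the randomized groups. If counseling persuaded hesitant people who then vaccinate later, the better arm could look slower.

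**Working it through.** **Inputs.** Text-arm uptake of 28% by day 60 (Sections 9.2 and 9.2.1; 20% + 8% = 28%); 200 per arm (Section 9.2.1); ascertainment to day 90 (Sections 4.3.5 and 7.2.1.1); 6-month uptake (Section 3.2 only). Everything beyond day 60 is extrapolation, because the protocol states one rate at one time point.

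**Step 1: day 60, no extrapolation.** A median needs at least 100 of 200 vaccinated. If the true rate is 28%, the binomial probability of that is about 4 × 10⁻¹¹.

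**Step 2: day 90, constant hazard assumed.**
- Hazard: h = −ln(1 − 0.28)/60 = 0.3285/60 = 0.005475 per day.
- Uptake at day 90: 1 − exp(−90h) = 1 − 0.72^1.5 = 38.9%.
- Median: ln 2/h = 0.6931/0.005475 = 126.6 days.
- Probability of at least 100 of 200 vaccinated when the true rate is 38.9%: about 0.0009.

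**Step 3: acceleration needed to reach 50% by day 90.** The hazard in days 60 to 90 would have to be −ln(0.50/0.72)/30 = 0.3646/30 = 0.01215 per day, and 0.01215/0.005475 = 2.2 times the earlier hazard. The text arm receives its flyer at enrollment and its text at 4 weeks. No intervention is scheduled after that, although the 60-day survey could itself act as a prompt.

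**Step 4: 6 months.**
- Constant hazard, day 180: 1 − 0.72³ = 62.7% (63.3% at day 183).
- Hazard halved after day 60: 1 − 0.72 × 0.72^(0.5 × 120/60) = 1 − 0.72² = 48.2%.
- Break-even for 50% by day 180: (0.3646/120)/0.005475 = 0.56. The later hazard must hold at about 56% or more of the early one.

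**Step 5: sensitivity to hazard shape.** Weibull curves through the same point, F(t) = 1 − 0.72^((t/60)^k), text arm:

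| Shape k | Uptake, day 90 | Uptake, day 183 | Median (day) |
|---|---|---|---|
| 0.5 | 33% | 44% | 267 |
| 0.75 | 36% | 53% | 162 |
| 1 | 39% | 63% | 127 |
| 1.5 | 45% | 83% | 99 |
| 2 | 52% | 95% | 87 |
| 3 | 67% | >99% | 77 |

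Of these shapes, only the strongly accelerating ones (2 and 3) reach half by day 90; only the strongly slowing one (0.5) misses at 6 months.

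**Step 6: what the alternatives show, for illustration only.** Take 38% by day 60 in the counseling arm (28% plus the 10-point detectable difference; not a forecast). The hazard is −ln(0.62)/60 = 0.007967.
- All randomized, restricted mean time unvaccinated to day 60, F(60)/h: 0.28/0.005475 = 51.1 days against 0.38/0.007967 = 47.7 days, a difference of 3.4 days.
- Only those vaccinated by day 60, median time: −ln(1 − 0.14)/0.005475 = 27.5 days against −ln(1 − 0.19)/0.007967 = 26.4 days, a difference of about 1 day.

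A 10-point difference in uptake nearly vanishes in the responders-only median. The text-arm result in Steps 1 to 5 does not use the 38%.

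**The case against.** A reader might infer that the endpoint cannot be estimated as planned. The documents do not support that, for four reasons.

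- **Horizon.** Section 3.2 does not tie the median to 90 days, and the line above it lists 6-month uptake. With that look-up, the constant-hazard median (day 127) falls inside follow-up. The 48.2% figure rests on a halving of the hazard that has no source in the protocol, and it lies within one standard error of 50% (√(0.482 × 0.518/200) = 3.5 points).
- **Counseling arm.** It is tempting to read 38% as the protocol's expectation and to quote a counseling-arm median of day 87. The 10 points are a detectable difference, so neither figure is a protocol forecast.
- **Population.** Nothing says that the median would be taken among the vaccinated only. That is a risk left open, not a stated plan.
- **Analysis detail.** The estimator, censoring rule and analysis set are commonly left to a statistical analysis plan, which is not at hand, so their absence is no fault here. A median reported as not reached is also a legitimate result of a time-to-event analysis.

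All four stand as limits on the claim. They do not remove it. The protocol itself fixes the median as the summary, its own rate makes that summary unlikely to exist in the text arm over the only follow-up its procedures describe, and the follow-up that might supply it is listed in one place and absent from the others.

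**Conclusion.** The point holds in limited form. An all-randomized median time to vaccination is not expected in the text arm within the 90-day procedures: about 39% vaccinated at day 90 at constant hazard, and about a 2.2-fold rise in hazard after day 60 needed to reach half. By 6 months it may or may not be reached, depending on whether the hazard holds at about 56% or more of its early level. The conclusion rests on the protocol's 28% by day 60 and, past that day, on assumed hazard shapes. No conclusion is drawn for the counseling arm.

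The consequence is minor. One secondary endpoint may return no usable contrast; the primary comparison is untouched.

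**What to change.** 1. Reconcile Section 3.2, Table 3, Section 4.3.5 and Section 7.2.1.1 on whether registry or record status is looked up at 6 months.
2. Restate the endpoint as time to RSV vaccination in all randomized participants, measured from randomization. State the origin explicitly, because Table 1 counts the primary endpoint's time frame from the intervention, whose timing differs between the arms.
3. Compare the arms with cumulative incidence curves and a log-rank test or hazard ratio, plus restricted mean time unvaccinated to a stated horizon: day 90, or 6 months if that look-up is run. Report the median only if it is reached.

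The cost is a change of wording and a small amount of extra analysis. There is one practical condition. Section 7.2.1.1 speaks of vaccination status, so the date of vaccination must also be taken from the registry, the medical record or the pharmacy proof.

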**Table 3: Study Overview**

Aim	Study Population	Study Design and Intervention	Outcomes
1	1. Community Advisory Group: 1a. Latino adults $\geq 60$ yr 1b. Latino adults 18-50 yrs. N~35 2. Anonymous Community Vaccine Hesitancy Survey (18+ years)	1. Adaptation of intervention components using ADAPT-ITT framework. Includes in-depth interviews and formation of community advisory groups for 1a and 1b. 2. Predictors of vaccine hesitancy	Developmental Aim Products Primary : Adapted intervention components Secondary : Publication on ADAPT-IT process of adapting core-intervention components
2	400 Latino adults $\geq 50$ years, who have not received the RSV vaccine	Motivate Trial: Randomized Trial with 2 groups 1. Flyer & text-message nudge from CBO 2. Flyer & text-message nudge from CBO AND CHW counseling	Primary : RSV vaccine uptake at 60 days per CAIR Secondary : RSV vaccine uptake at 60 days per self-report; RSV vaccine uptake at 90 days per CAIR; appointment made at 60 days in clinic or pharmacy with intent to get RSV vaccine; median time to vaccination; increase in RSV vaccine confidence; increase in motivation to get RSV vaccine; increase in RSV vaccine knowledge; average proportion of social network contacts $\geq 50$ with whom participant discussed RSV vaccination at 60 days; implementation outcomes per the RE-AIM framework
3	350 adults, 18-50 with stratified sampling by age-group.	Activate Trial: Randomized Trial with 2 groups 1. Flyer & text-message nudge from CBO 2. Flyer & text-message nudge from CBO AND CHW ‘activation’ counseling	Primary : Average proportion of social network contacts $\geq 50$ with whom participant discussed RSV vaccination at 60 days (referred to as ‘Activation’) Secondary : Implementation outcomes per RE-AIM framework; increase in RSV vaccine confidence; increase in motivation to discuss the RSV vaccine with eligible family members or friends; increase in RSV vaccine knowledge; discussed RSV vaccination with $\geq 1$ $\geq 50$ -year-old at 60 days

**Qualitative Studies for Aim 2 and 3: In-depth interviews** from participants in each group including those who meet the primary outcome and those who do not  
**Focus Groups:** CHWs, key stakeholders focusing on implementation outcomes

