**Arm 1- Text message nudge**

**Arm 2: CHW counseling and text message nudge**

### 7.2.1.1. Procedures Aim 2

**Baseline survey:** After providing informed consent, participants will complete a 30 minute baseline survey, which will include questions on demographics, knowledge of RSV and the RSV vaccine, vaccine confidence, acculturation scale. We will use the standardized vaccine hesitancy scale and BeSD vaccine hesitancy scale.

**Intervention delivery:** The schedule of interventions is outlined in Figure 6 and outlined in the Schedule of Activities in **Section 7.3**. With texts sent 4 weeks post-enrollment in both arms and the CHW counseling within 2 weeks of enrollment.

**Endpoint survey:** Participants will receive a 60-day endpoint survey with similar questions to those asked at baseline: vaccine confidence, BeSD framework core-questions, self-reported vaccination status and location, location of vaccination, self-reported number of discussions of RSV vaccination with people  $\geq 50$  years, proportion who received text message. We will also assess implementation-specific factors: (1) Process measures (e.g. text messages received, access-related challenges in getting vaccinated, called LTF hotline), location of vaccination, access-related barriers to vaccination (i.e. challenges making an appointment) and (2) Pathways: (a) whether the interventions elicited responses along the intended pathways, e.g. did the text message positively *reinforce* or remind people to take action on intended behavior, did CHW counseling improve trust and perceptions of RSV susceptibility and (b) assess subjective rating or satisfaction of interventions by participants with Likert-style questions.

[figure not shown]
**Process Metrics/CHW log:** CHW will enter the following process measures into a log that will be entered in REDcap: fidelity to counseling script, time for each motivation session, perceived client-specific barriers and facilitators, number of calls received or made for navigation and counseling.

**Text message receipt confirmation:** Text-messages will be sent 4 weeks post-enrollment. Successful receipt will be assessed retrospectively via Twilio and self-report of reading the text will be assessed at the time of the endpoint questionnaire.

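### Scoring confidence, motivation and knowledge as a 1-point rise builds in a ceiling and costs power, although the graded scores are already collected

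*Protocol*

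**What the plan says.** The Aim 2 list in Protocol section 3.2 has "Increase in RSV Vaccine confidence (BeSD indicator) by 1 point", "Increase in motivation to get RSV Vaccine (BeSD indicator) by 1 point" and "Increase in RSV vaccine knowledge by 1 point (Likert scale". The Aim 3 list has the same confidence and knowledge outcomes, and a motivation outcome about discussing the vaccine with others, also by 1 point. The knowledge item has four levels, "1 = nothing, 2= a little, 3= some, 4= a lot". The range of the BeSD items is not given, and no rule is stated for participants who start in the top category.

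The graded answers are collected twice. Section 7.2.1.1 says "Participants will receive a 60-day endpoint survey with similar questions to those asked at baseline: vaccine confidence, BeSD framework core-questions", and section 7.2.2.1 has baseline and endpoint surveys for Aim 3 that cover vaccine confidence.

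Section 9.2 analyses secondary outcomes by an approach analogous to the primary, which is tested "for the primary outcome of vaccine uptake using the Fisher exact test" and then estimated with TMLE adjusted for stratification factors and baseline predictors. Sections 9.2.1 and 9.3.1 express power for secondary outcomes in percentage points, and 9.3.1 refers to binary outcomes. It is therefore natural to read the 1-point rise as a yes/no result for each participant.

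**The concern.** Three things are lost when a short ordinal item is cut this way.

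- **Ceiling.** A participant who answers 4 on the knowledge item at baseline cannot rise. With no other rule, that person is a non-responder in either arm, whatever the intervention does. Any bounded BeSD item behaves the same way.
- **Direction.** A participant who falls from 3 to 1 is scored like one who stays at 3.
- **Size.** A move from 1 to 4 is scored like a move from 1 to 2.

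At stake is the precision of the between-arm comparison on these outcomes. The more participants start at the top, the smaller the group in which a difference can appear, and the easier it is to read a null result as no effect on confidence or knowledge.

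**Working it through.** **The plan's own figure.** Section 9.2.1 gives a detectable ITT difference of 10.6 points for secondary outcomes with 10% lost, which leaves 200 × 0.9 = 180 per arm. At the only control rate stated (28%, for vaccine uptake), with two-sided 5% and 80% power, the difference is about (1.96 + 0.84) × √[(0.28×0.72 + 0.42×0.58)/180] = 2.80 × 0.0497 ≈ 0.14, or 14 points. The stated figure is not reproduced. That is a matter for the sample-size section and is not used below, because no control rate is given for the 1-point outcomes.

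**How the cut scores participants (knowledge, 1 to 4).**

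| Baseline → day 60 | Change | 1-point outcome |
|---|---|---|
| 1 → 2 | +1 | success |
| 1 → 4 | +3 | success |
| 3 → 3 | 0 | failure |
| 3 → 1 | −2 | failure |
| 4 → 4 | 0 (cannot rise) | failure |

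**Inputs to the power comparison.** From the protocol: four levels (section 3.2), and 180 per arm (section 9.2.1 with 10% loss). Assumed, because the protocol is silent: a 0.3 SD latent shift between arms, a 0.3 SD rise common to both arms, a baseline to day-60 correlation of 0.5 to 0.7, and 10%, 25% or 40% in the top category at baseline, with the lower levels split equally.

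**Method.** Draw latent bivariate normal scores and cut both at the same thresholds into four levels. Run 2,000 trials per setting with two-sided 5% tests. The analyses compared are (a) rise of at least 1, unadjusted; (b) rise of at least 1, adjusted for baseline category; and (c) day-60 score adjusted for baseline score. Analysis (b) stands in for the planned TMLE. Type I error was near 5% for (b) and (c). Simulation error at 65% power is √(0.65×0.35/2000) ≈ 1 point.

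| At ceiling at baseline | (a) 1-point, unadjusted | (b) 1-point, adjusted | (c) Score, adjusted |
|---|---|---|---|
| 10% | 57-73% | 65-81% | 85-93% |
| 25% | 43-62% | 54-75% | 81-91% |
| 40% | 29-41% | 48-63% | 76-83% |

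In each cell the lower figure is for correlation 0.5 and the higher for 0.7.

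**Like-for-like gap, (c) minus (b).** 10%: 85−65 = 20 and 93−81 = 12 points. 25%: 81−54 = 27 and 91−75 = 16. 40%: 76−48 = 28 and 83−63 = 20. The gap is 12 to 28 points.

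**As information.** The ratio is [(1.96 + z of power b)/(1.96 + z of power c)]². For 10% at ceiling and correlation 0.5 it is [(1.96+0.39)/(1.96+1.04)]² = 5.52/9.00 = 0.61. For 40% and 0.5 it is [(1.96−0.05)/(1.96+0.71)]² = 3.65/7.13 = 0.51. For 10% and 0.7 it is [(1.96+0.88)/(1.96+1.48)]² = 8.07/11.83 = 0.68. The other three settings lie between 0.51 and 0.68. Under these assumptions the cut keeps roughly half to two thirds of the information.

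**Is it the cut or the adjustment?** A plain change score with no adjustment had 55-86% power across the same settings, above (b) in every one. The cut itself is therefore a large part of the loss.

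**The case against.** A responder definition is a legitimate endpoint and is easy to explain to community partners. An SAP that is not shown may add a ceiling rule or an analysis of the graded score. Because the full scores are kept, nothing is lost at the design stage. All of this stands and lowers the priority. It does not remove the point, because the outcome definition itself is fixed in the protocol.

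Four stronger readings are tempting, and the documents do not support them.

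- **That the loss is as large as columns (a) and (c) suggest.** Section 9.2 plans TMLE with baseline predictors and carries the approach over to secondary outcomes. The baseline score is an obvious predictor, though it is not named. The fair comparison is (b) with (c); adjustment recovers part of the gap.
- **That these outcomes carry the mechanism claim.** Section 9.2 assigns mechanism to mediation analyses using post-baseline trust and perceived benefits, with no 1-point cut stated.
- **That section 3.1 contradicts section 3.2.** Section 3.1 says "Secondary outcomes include change in motivation to get and confidence in the RSV vaccine" and Table 3 lists "increase in RSV vaccine confidence; increase in motivation to get RSV vaccine; increase in RSV vaccine knowledge". A 1-point rise is one way to measure change, so these are summaries of the same outcomes.
- **That a real effect is likely to be missed.** This would need many participants at the top at baseline. Nothing in the protocol supports 25-40%. Aim 2 enrols only unvaccinated people, and section 1.1 reports lower RSV vaccine confidence among older Latinos. With few at the top the loss is smaller: with 5% at ceiling, the unadjusted 1-point outcome loses about 11-24% of information against a plain change score.

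**Conclusion.** The point holds as a matter of analysis efficiency. The ceiling, the equal scoring of falls and no change, and the disregard of the size of gains follow directly from the definition in section 3.2 and need no assumption beyond reading it as a yes/no result per participant. With baseline adjustment on both sides, the power cost is 12 to 28 percentage points under the assumed 4-level item, 180 per arm, 0.3 SD latent shift, correlation 0.5 to 0.7 and 10-40% at ceiling. Its direction was the same in every setting tried, and it was larger on the information scale when more participants started at the top. Its true size is unknown, since the protocol gives none of the assumed quantities. It concerns secondary outcomes only, so this is a low-to-moderate priority improvement.

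**What to change.** In section 3.2, for both trials, define each confidence, motivation and knowledge outcome as the day-60 score. Name the between-arm comparison of that score, adjusted for its baseline score, as the main analysis; an ordinal model, a linear model or TMLE on the score would each serve. Keep the proportion with a 1-point rise as a descriptive summary, reported by arm with the share in the top category at baseline. Use the same definition in section 3.1 and Table 3 for consistency.

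The cost is wording only: no added data, visits or participants. The downside is a slightly less simple headline figure than a percentage improved, which the descriptive summary still supplies.
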